2. HYPOTHESIS AND OBJECTIVES

Specific aim 1: To assess the effectiveness of MPI, versus standard care, in improving adherence to IVT follow-up appointments at 6, 12 and 18 months (main timepoint for primary outcome) *in patients with nAMD and DME requiring long term management* (primary outcome).

Hypothesis 1: *Compared to those in standard care, patients in the MPI group will have higher adherence to long-term follow-up appointments and IVT therapy.*

Specific aim 2A: Assess the effectiveness of MPI, versus standard care, in improving domain-specific CAT scores at the various follow-up timepoints (secondary outcome).

Hypothesis 2A: *Compared to those in standard care, patients in the MPI group will have greater gains in domain-specific CAT scores at each follow-up time point.*

Specific aim 2B: Assess the effectiveness of MPI versus standard care in improving visual acuity (VA), contrast sensitivity (CS), disease free intervals between IVT (as measured on optical coherence tomography (OCT) (secondary outcomes).

Hypothesis 2B: *Compared to those in standard care, patients in the MPI group will have greater VA and CS gains and achieve longer disease-free intervals between IVT at each follow-up time point.*

Specific Aim 3: To assess implementation outcomes of the MPI such as acceptability, adoptability, appropriateness, feasibility, fidelity.

Hypothesis 3: *Using a mixed methodology, with quantitative and qualitative outcome measures as reported by patients, caregivers, clinicians, nurses and allied health professionals, MPI will be an appropriate, adoptable, acceptable, feasible intervention with good fidelity.*

Specific Aim 4: To assess the cost-effectiveness of the MPI for improving adherence to IVT, considering its potential impact on long term visual acuity (VA) loss and QoL adjusted years (QALYs)

Hypothesis 4: *The MPI is incrementally cost-effective relative to standard care, based on accepted willingness-to-pay thresholds⁴².*

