- Following baseline assessment, **participants with suboptimal CAT scores (Cohort 1-<50 in any domain)** will be included in the RCT and randomly allocated in a 1:1 ratio to either the intervention group (personalised multi-disciplinary protocolised intervention, MPI) or the control group (standard care). Randomisation will be conducted using a computer-generated random sequence created by an independent biostatistician not involved in recruitment or outcome assessment. To ensure balance across disease types, randomisation will be stratified by diagnosis (neovascular age-related macular degeneration [nAMD] vs. diabetic macular edema [DME]). Allocation concealment will be maintained using sequentially numbered, opaque, sealed envelopes prepared by an independent study coordinator. The envelopes will only be opened after baseline data collection to assign participants to their respective groups. Co-Is that are not treating clinicians and data analysts will remain blinded to group allocation, although masking of participants and principal investigator and Co-Is who are the treating clinicians will not be feasible due to the nature of the intervention.

- For the MPI arm, the CAT scores integrated into the electronic medical records will be used to formulate **an automated protocolized standardized MPI for all patients based on the domain specific scores that are sub-optimal** (See **Table 2**). All MPI patients will receive *a medical consultation (compulsory) and an addition of Intervention 1-4 (electives, 1) NE, 2) OP, 3) OT, 4) SW*. In the MPI arm, these referrals would be automatically triggered by the study team based on baseline CAT scores and the treating clinician will be informed. The MPI visits will take place on the same day as standard clinical visits where possible, however additional MPI study visits may be needed if there are scheduling challenges. Referral adherence to the MPI appointments and intervention will be assessed.

Sub-optimal scores are defined as any domain where the scores are below 50 at baseline or have reduced by 25% from the baseline visit. Table 2 summarizes the MPI interventions that are relevant to each CAT domain. A tailored MPI will be formulated and recommended to the patient at baseline, or at a follow-up time-points where domain scores decrease, and the MPI should be completed within 4 months.

Table 2: Standardised personalised MPI based on sub-optimal CAT domain-specific scores

| Ret CAT | | MacCAT | |

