At each follow up time point, based on the previous scheduled follow-up appointments and recommended IVT schedule, the study team will assess if the patient has been “adherent” or “non-adherent”. If the patient does not visit the clinic within the range of the follow-up time points or does not attend the scheduled study visit, phone calls will be made to determine reasons or barriers for adherence. A remote invitation to complete the CAT questionnaire will also be sent to these patients or if uncontactable, they will be approached and interviewed at their next clinical visit. For previously treated patients, previous adherence status up to 2 years prior to study enrolment for the time of IVT treatment will be recorded by the study team from medical records.

Secondary outcome measures will be assessed at baseline and 6, 12, and 18 month follow up visits (+/- 8 weeks) including:

- CAT scores (Specific aim 2A) from the CAT questionnaire database
- Visual function -Monocular and binocular presenting corrected VA and CS (Specific aim 2B) will be collected from the clinical records. If data are not present, the CRCs will conduct these tests on participants using standardized protocols.
- Disease free intervals as defined by the maximum IVT treatment interval where no disease activity recurrence is detected on OCT will be collected from clinical records and OCT images from the clinical database (Specific aim 2B)
- Tertiary outcome measures include the acceptability, adoptability, appropriateness, feasibility, fidelity through mixed method testing with interviews and questionnaires (Specific aim 3).
- The costs of MPI, baseline and 18-month assessment of Euro-quality of life (EQ-5D) to assess QALYs (Specific aim 4)

Qualitative and quantitative analysis of key stakeholders (Specific aim 3)

The PI, assisted by their Co-Is and collaborators, will identify eligible individuals for qualitative interviewing that will be performed with major stakeholders between 6 to 15 months timeline. These include the clinicians, nurses and the allied health specialists (OP, OT and SW) who will be involved in administering the MPI, and patients and care-givers who receive the MPI. Potential individuals will be contacted over email or phone call, and a trained study team will follow up on affirmative responses by obtaining written informed consent to carry out the following study procedures:

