Qualitative protocol: Semi-structured (1-on-1) interviews with the above key stakeholders will be conducted to explore their perspectives on barriers and enablers of integrating MPI into a Singapore public hospital for the management of nAMD and DME patients receiving IVT. Purposive and snowball sampling will be used to ensure all stakeholder groups are represented. Interviews will be conducted until no new data emerges.

An interview guide will be developed, underpinned by a suitable implementation research framework such as the NASSS framework (the non-adoption, abandonment, scale-up, spread, and sustainability framework)⁶⁰ which was created for planning and investigating implementation of health interventions. We will include interview questions that help elicit stakeholder perspectives on implementation outcomes salient to future implementation success, e.g. adoption, acceptability, appropriateness, feasibility, and fidelity, as defined by Proctor et al 2011⁶¹.

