8.2. Statistical and Analytical Plans

Specific aim 1: Planned statistical analysis for the primary outcome measure will be the difference in percentage of adherence rate between the standard care and MPI arm assessed by the chi-square test or Fisher's exact test. Cox proportional hazards model will be used to assess the independent effect of MPI on adherence rates, after adjusting for age, baseline CAT scores, visual function, anatomical outcomes, type of IVT medication given, and disease-free intervals.

Specific aims 2A and 2B: CAT scores will be assessed with a two-sample t-test to compare the differences in mean CAT scores between the 2 arms. Linear mixed models will be used to assess the independent effect of MPI on follow-up CAT scores, after adjusting for fixed effects terms such as age, baseline CAT scores, visual function, anatomical outcomes, type of IVT medication given, and disease-free intervals, and a random slope term follow-up time (measured in months).

Specific aim 3 Interviews will be conducted in-person or online, audio-recorded, and transcribed verbatim by professional transcribers (i.e. transcriptions outsourced to third party). Designated researchers in the study team will check a random 10% sample of interview transcriptions for accuracy, prior to qualitative data analysis. If errors or inaccuracies are found in the random sample of transcripts, then 100% of the transcripts will need to be checked and edited for accuracy, prior to data analysis. We will analyse the qualitative data as per Gale et al's thematic analysis⁶². NVivo software will be used to manage qualitative data analysis. A standardised questionnaire to assess implementation outcomes will also be administered to all the stakeholders for a quantitative assessment.

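### Fidelity of the MPI is measured only by stakeholder report, although the MPI has checkable delivery rules and the referral-adherence data promised in the protocol are used in no aim or analysis

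*Protocol*

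**What the plan says.** Four places in the protocol describe how fidelity is to be assessed.

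- Section 2, Hypothesis 3, expects good fidelity on the basis of "quantitative and qualitative outcome measures as reported by patients, caregivers, clinicians, nurses and allied health professionals".
- Section 5, study schedule and outcome measures, lists the tertiary outcomes as "acceptability, adoptability, appropriateness, feasibility, fidelity through mixed method testing with interviews and questionnaires (Specific aim 3".
- Section 5, qualitative protocol: "We will include interview questions that help elicit stakeholder perspectives on implementation outcomes salient to future implementation success". Fidelity is one of the examples that follow.
- Section 8.2, Specific aim 3, adds the quantitative part: "A standardised questionnaire to assess implementation outcomes will also be administered to all the stakeholders for a quantitative assessment".

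Section 5 also sets out what delivery of the MPI consists of. Every MPI patient has a compulsory medical consultation. Table 2 maps each sub-optimal CAT domain to one or two of four services, and "these referrals would be automatically triggered by the study team based on baseline CAT scores and the treating clinician will be informed". The MPI is meant to be finished within 4 months. The same part of Section 5 states: "Referral adherence to the MPI appointments and intervention will be assessed". That sentence is not repeated in the outcome list, is attached to no specific aim, and has no analysis in Section 8.2.

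**The concern.** For a protocolised intervention, fidelity is first a factual matter: were the prescribed components provided, and were they provided on time? Interviews and questionnaires answer a different question, namely how well the people involved think it went. Both are worth having, but only the first can support a claim that the MPI was delivered as designed.

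The interview sample makes the gap wider. Section 5 draws it from staff who administer the MPI and from patients and caregivers who receive it, by purposive and snowball sampling, with follow-up of those who respond favourably to the invitation. Staff would be commenting on their own delivery, and patients who never attended a triggered referral are probably the hardest to reach.

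At stake is whether the fidelity part of Hypothesis 3 means what it says. As written, good fidelity could be concluded from favourable reports while a substantial share of triggered referrals was never issued or never completed. Section 1 makes the implementation outcomes central to planning any scale-up, so a reader of the results would take the fidelity claim at face value.

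**Working it through.** No formula applies and the protocol gives no figure for fidelity, so the check sets the text on measurement beside the text on delivery.

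**Step 1. Is any source other than stakeholder report named for fidelity?** Hypothesis 3 relies on reported measures. The outcome list names interviews and questionnaires. The interview guide seeks perspectives. Section 8.2 analyses Aim 3 through thematic analysis of transcripts and a questionnaire given to stakeholders. All four agree and none mentions delivery records. Mixed methods here means interviews plus a questionnaire.

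**Step 2. Is there a standard against which delivery could be checked?** Yes, in three parts, all in Section 5:

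| Delivery rule | What a record would show | What stakeholder report shows |
|---|---|---|
| Compulsory medical consultation | Given or not, per patient | Whether it was recalled or valued |
| Referrals triggered under Table 2 | Issued or not, per service | Whether staff believe the scheme was followed |
| Completion within 4 months | Completed in time or not, per referral | An impression of timeliness |

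**Step 3. Does a denominator exist?** Yes. Patients enter the RCT because at least one domain is sub-optimal, and every domain in Table 2 leads to at least one service. Each MPI patient therefore has at least one triggered referral. The four services are nurse education (1), low vision optometry (2), occupational therapy (3) and social work (4). On either instrument, sub-optimal lighting alone triggers one service (2). Sub-optimal activity limitation together with the emotional domain triggers all four (2 and 3, plus 1 and 4). One assessment thus yields between 1 and 4 distinct referrals per patient, and referrals are clustered within patients.

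**Step 4. Are delivery data foreseen?** In part. The protocol says that referral adherence will be assessed. It does not say what is recorded, what the denominator is, or what counts as completion, and it does not mention recording whether each Table 2 referral was issued or the consultation given.

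**Step 5. Would records be out of keeping with the rest of the plan?** No. Adherence to intravitreal treatment is judged against scheduled appointments and the recommended treatment schedule. Visual acuity, contrast sensitivity and disease-free intervals come from clinical records. Fidelity is an exception in relying on report alone.

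The stated method therefore measures perceived fidelity. The promised data that come closest to actual delivery are connected to nothing.

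**The case against.** The strongest reply has four parts.

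- **The text is not exclusive.** The tertiary measures are said to include these outcomes, and a statistical analysis plan may define the referral-adherence table. It is true that denominators and table layouts belong there. But the protocol itself fixes the source of the fidelity measure, in four consistent places, and that source is report.
- **The definition of fidelity is open.** The protocol takes its implementation outcomes from a cited source that is not available here, and the MPI is recommended to patients, not imposed on them. A patient who declines a correctly issued referral shows low uptake, not poor delivery by staff. This stands: a single completion rate would mix the two, so they should be reported separately.
- **The data may be collected anyway.** If referral adherence is assessed, investigators can look at it whatever it is called. This stands in part. A reader might infer that a null primary result could not be interpreted at all. The documents do not support that. They show only that no delivery analysis is planned to help with it.
- **The outcome is tertiary.** This stands, and it limits the weight of the point.

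Three further inferences are tempting but unsupported. First, a reader might argue from the indicative 40 interviews that fidelity would be estimated imprecisely. Those interviews run to thematic saturation and do not estimate a proportion, and the questionnaire goes to all stakeholders, a number that the protocol does not give. The problem is validity, not precision. Second, a reader might think that the Aim 4 costing is undermined. Section 8.2 takes resource use and costs in the first 18 months from the study itself, and nothing feeds perceived fidelity into the model. Third, a reader might take it that completed referrals are already recorded. Section 5 says only that referral adherence will be assessed.

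**Conclusion.** The point holds. The protocol makes a claim about fidelity and fixes a method that measures perceptions of it, while leaving its own delivery rules and its own referral-adherence assessment outside every aim and analysis. This is a choice of a weaker measure where a better one is close at hand, and it should be changed.

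Its size is limited. The outcome is tertiary and descriptive, and the protocol sets no threshold for good fidelity, so no formal test is at risk. The primary analysis, the sample size and participant safety are unaffected. The gain is a fidelity statement that rests on what was delivered, and a planned delivery summary to read beside the primary result, especially if that result is null.

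The conclusion assumes that fidelity is meant to cover delivery of the components in Section 5 and Table 2, and that no unseen document already ties referral adherence to Aim 3.

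**What to change.** In the outcome list of Section 5 and under Specific aim 3 in Section 8.2, define fidelity among MPI-arm patients from delivery records, and report separately:

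- (a) the proportion of patients given the compulsory consultation;
- (b) the proportion of Table 2-triggered referrals that were issued, overall and by service;
- (c) the proportion of issued referrals completed within the stated 4 months, overall and by service, labelled as patient uptake;
- (d) the proportion of patients with the consultation and all triggered referrals completed.

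Give each a 95% confidence interval. Measures (a) and (d) have one observation per patient, so an ordinary binomial interval serves. Measures (b) and (c) can have several referrals per patient, so use an interval that allows for this, such as a cluster-robust interval or a bootstrap that resamples patients. Count one referral per service when several domains point to the same service. State which date starts the 4 months, and whether referrals triggered at follow-up visits count. Section 5 ties the triggers to baseline scores in one sentence and allows an MPI at later time points in another, so the two must be reconciled before the denominator is fixed.

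Keep the interviews and questionnaire for acceptability, appropriateness, perceived feasibility and reasons for non-delivery.

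The cost is a change of wording, one descriptive table, and little or no extra data capture (whether the consultation was given, and issue and completion dates for each referral). The fidelity figure may turn out less favourable than stakeholder report would suggest.

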|---------------------|---------------|---------------------|---------------|
| Item Bank | Interventions | Item Bank | Interventions |
| Visual symptoms | (2) | Activity Limitation | (2), (3) |
| Activity Limitation | (2), (3) | Lighting | (2) |
| Emotional | (1), (4) | Emotional | (1), (4) |
| Health Concerns | (1), (4) | Concerns | (1), (4) |
| Convenience | (1), (4) | AMD management | (1), (4) |
| Lighting | (2), | | |
| Social | (4) | | |
| Economic | (4) | | |

- In the standard care arm, the treating clinician will be masked from the CAT scores and will use his/her own discretion when recommending the treatment regimen or when making any appropriate nurse or allied health referrals, independent of the CAT scores. The CAT scores will be recorded by the clinical research coordinator at baseline and follow-up visits for comparison to the MPI arm.
- For those patients who do not have sub-optimal CAT scores at baseline, they will be assigned to an observational study group (Cohort 2) to continue to undergo routine clinical care and at the assigned study time points, they will be reassessed for any changes in their CAT scores and will undergo randomisation into the RCT if their scores have dropped below 50 or have reduced by 25% from the baseline visit. For those patients who do not experience sub-optimal CAT scores or a significant drop in their CAT scores during the duration of the study, they will still have their data collected at

all study visits based on the protocol but will not undergo randomisation. If any of these cohort patients show non-adherence to clinic visits during the duration of the study, they will be eligible for “rescue” MPI according to the clinician’s discretion at their next study visit and will be analysed as a separate sub-group.

Study schedule and outcome measures

The primary outcome is the comparison of adherence rates to IVT treatment between the MPI arm versus standard care (Cohort 1) at 6, 12 and 18 month time points (+/- 8 weeks) (main outcome) (Specific aim 1). The follow-up study visits will be coordinated with the planned clinical standard care visits, only if the patient does not have a routine clinical care visit scheduled within the range of the follow-up time-points will an additional study visit be scheduled.

Adherence is defined as

- 1) patient attends all follow-up appointments within 1 month of the planned follow up date, and
- 2) patient receives IVT within 1 month of when the doctor recommends IVT.

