8. SAMPLE SIZE AND STATISTICAL METHODS

8.1. Determination of Sample Size

Specific Aim 1 and 2: The primary outcome comparison of adherence rates to IVT treatment between the MPI arm versus standard care at various follow-up time points with 18 months as the main time point. It is estimated that the baseline non-adherence rate with standard care arm is 40% (SD=2). Considering a reduction of the non-adherence rate to 20% as a clinically significant difference, and assuming a power of 80% and a two-sided level of significance at 5%, the minimum sample size

required is 79 patients per arm (rounded up to 160 patients in total). Assuming a maximum 20% dropout in the study we estimate a sample size of 200 patients (Specific aim 1).

For secondary outcomes such as the improvement of QoL as assessed by the various CAT domain scores, we assume a modest effect size difference of 0.5 between the two arms. Using a power of 80%, a two-sided level of significance at 5%, and the maximum 20% dropout rate, we estimate the required sample size is 158 (79 per arm) (Specific aim 2A). Hence, this is included in the larger sample size calculated above.

Specific aim 3: There is no *a priori* sample size required for qualitative interviews. We will continue our semi-structured interviews until thematic saturation is reached (i.e. no new themes emerge). Based on previous studies by our group^{31,67}, we anticipate the need to interview between 5-10 participants for each stakeholder group to obtain data saturation, broadly: (a) clinicians using CATs and MPI, (b) NE, OP, OT and SW involved in administering MPI (c) patients involved in this study, and (d) caregivers of patients. For the purposes of estimating a budget for this grant proposal, we state an indicative sample size of 40 interview participants i.e. 10 in total for stakeholder group a and b, and 30 for stakeholder group c and d (patients and caregivers).

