Specific aim 4: To assess the cost-effectiveness analysis of the MPI, we will develop a cohort-based Markov model embedded within a decision tree to simulate the net lifetime cost and effectiveness of the MPI compared to standard care. The model's health states will be defined by VA ranges, consistent with prior cost-effectiveness studies for of macular disease treatments^{63,64}. We will quantify the incremental costs of implementing the MPI using an activity-based costing approach, which includes all non-sunk costs – such as labour, materials and supplies, and amortized technology and rental costs – associated with treating each patient. These costs will be categorized by key activities, including physician/nurse/allied health training, CAT assessment, and referral to personalized programs. Treatment costs will be based on non-subsidized bill sizes, which are expected to approximate actual costs. Data on health resource utilization and costs incurred during the first 18 months will come from this study. For benefits, which are measured in terms of QALYs gained, QoL weights will be measured for month 18 using the EQ-5D instrument and validated local preference weights⁶⁵. The key difference between the MPI and standard care will be the proportion of IVT-adherent patients, influencing costs and long-term VA outcomes. As these differences likely persist over a patient's remaining lifetime, the model will extrapolate long-term VA and corresponding quality-of-life weights based on published trajectories for treated (adherent) and untreated (non-adherent) patients⁶⁶. With each subsequent annual cycle, the surviving cohort will accrue costs and QALYs associated with their VA and IVT adherence status. This model will be used to estimate the incremental cost-effectiveness ratio (ICER) for the MPI. We will also conduct one-way and n-way sensitivity analyses for all key model inputs and present cost-effectiveness acceptability curves showing the probability that the MPI is cost-effective at various willingness-to-pay thresholds policymakers may consider. We will also conduct scenario analyses to investigate the robustness of our results to alternative assumptions on long-run VA trajectories.

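### EQ-5D is taken only at baseline and month 18, and the remote route for missed visits names only the CAT, so a patient who misses month 18 has no follow-up utility for Aim 4

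*Protocol*

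**What the plan says.** Protocol Section 5 (study schedule and outcome measures) sets the EQ-5D schedule as "The costs of MPI, baseline and 18-month assessment of Euro-quality of life (EQ-5D) to assess QALYs (Specific aim 4"). The same list places CAT scores and visual function at baseline and at months 6, 12 and 18, each follow-up with a window of 8 weeks either side.

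Section 8.2 (Specific aim 4) states that "QoL weights will be measured for month 18 using the EQ-5D instrument and validated local preference weights". It describes a cohort Markov model with states defined by visual acuity. The cohort accrues QALYs according to acuity and adherence status, and long-term weights are extrapolated from published trajectories.

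For a patient who misses a visit, Section 5 provides three contacts. First, "phone calls will be made to determine reasons or barriers for adherence". Second, "A remote invitation to complete the CAT questionnaire will also be sent to these patients or if uncontactable, they will be approached". The third, for those who cannot be reached, is an interview when they next come to clinic. EQ-5D is named in none of them. Section 5 does arrange attendance at the time point itself by booking an extra visit where one is needed; the rule begins "only if the patient does not have a routine clinical care visit scheduled within the range of the follow-up time-points will an additional study visit".

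Section 8.1 plans for loss: "Assuming a maximum 20% dropout in the study we estimate a sample size of 200 patients".

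**The concern.** Month 18 is the only post-baseline EQ-5D reading. If it is missed there is no earlier follow-up value to fall back on, and the stated recovery route collects a different instrument. When a questionnaire is given, and to whom, is fixed by the protocol; an analysis plan can decide how to treat a missing value but cannot supply one that was never collected.

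The gap may well be informative. Under Section 5 an adherent patient attends every appointment within 1 month of the planned date. A patient with a clinic appointment planned around month 18 who has still not come when the 8-week window closes is more than 1 month late, and so non-adherent by definition. Adherence is also what Section 8.2 names as the main difference between the arms in the cost-effectiveness model. The trial's own weights could therefore describe attenders better than the patients whose adherence the MPI is meant to change.

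There is a second, smaller cost. Section 5 expects an MPI to be completed within 4 months. Two readings 18 months apart cannot show when a change in utility happened, so QALYs over the trial period rest on an assumed path.

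**Working it through.** **Inputs.** From Section 8.1: non-adherence 40% in standard care and 20% with MPI; dropout at most 20%; total 200. From Section 5: 1:1 allocation. I take the 200 as randomised patients, 100 per arm. The adherence mix of dropouts, the split of dropout between arms and all utility differences are not in the documents; they are assumed below and shown as ranges.

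**The plan's own figure.** Unpooled two-proportion formula: 2.80² × (0.4 × 0.6 + 0.2 × 0.8) / 0.2² = 78.49, so 79 per arm, which the plan rounds to 160 in total. 160 / 0.80 = 200. The stated size reproduces, and nothing in this point changes it.

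**How many readings could be lost.** 0.20 × 200 = 40 patients. Expected non-adherent patients: 40 + 20 = 60. If a share f of the 40 dropouts is non-adherent, 40f of the 60 have no month-18 EQ-5D, and the non-adherent share among the 160 observed is (60 − 40f)/160:

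| f (assumed) | Non-adherent patients missing | Non-adherent share among observed (30% in full) |
|---|---|---|
| 30% | 12 of 60 (20%) | 30.0% |
| 50% | 20 of 60 (33%) | 25.0% |
| 75% | 30 of 60 (50%) | 18.8% |
| 100% | 40 of 60 (67%) | 12.5% |

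Even in the last row, 20 non-adherent patients remain observed.

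**Direction, equal dropout.** With 20 dropouts per arm, d of them non-adherent in each arm, the completers' gap is [(40 − d) − (20 − d)] / 80 = 20/80 = 25 points, whatever d is.
- d = 10: 30/80 = 37.5% against 10/80 = 12.5%.
- d = 20: 20/80 = 25% against 0/80 = 0%.

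The planned gap is 20 points. With an assumed utility deficit of 0.05 to 0.10 for non-adherence, the full difference is 0.20 × deficit = 0.01 to 0.02, and completers show 0.25 × deficit = 0.0125 to 0.025. The difference is overstated.

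If dropouts instead mirror their own arm (8 non-adherent of 20 in control, 4 of 20 in MPI), completers show 32/80 = 40% and 16/80 = 20%, and there is no distortion.

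**Direction, unequal dropout.** If dropouts have utility lower than completers in their arm by an assumed 0.05 to 0.10, completers understate the difference by (control dropout − MPI dropout) × deficit:
- 25% v 15%, deficit 0.05: 0.10 × 0.05 = 0.005.
- 30% v 10%, deficit 0.10: 0.20 × 0.10 = 0.02.

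So the sign depends on facts the documents do not give, and the shift can be as large as the difference being measured.

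**Path between readings (illustration).** Suppose a gain of size G builds up linearly to month 4 and then holds. The true area is G × (4/2 + 14)/12 = 1.33G. A straight line from baseline to month 18 gives G × (18/2)/12 = 0.75G. With a reading at month 6 as well, it is G × (6/2 + 12)/12 = 1.25G. The shape of the path and the straight-line rule are assumptions.

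**The case against.** Several stronger readings are tempting, and the documents do not carry them.

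- **That the patients lost are mostly non-adherent.** Section 8.1 gives 20% as a planning maximum and says nothing about who leaves. A patient more than 1 month late for an injection can still attend month 18, given the window and the additional study visit. Likely to include non-adherent patients is as far as the text goes.
- **That the QALY difference is biased towards zero.** With equal dropout and equal numbers of non-adherent dropouts per arm, the gap among completers grows. Understatement needs heavier loss in control, which is an assumption.
- **That the lifetime cost-effectiveness result is undermined.** The model uses acuity-based states, takes adherence from appointment and treatment schedules rather than from EQ-5D, and draws its long-term weights from published trajectories. Section 8.2 also plans one-way, n-way and scenario analyses. The crude arm comparison of month-18 utility worked above is an illustration, not the planned analysis.
- **That missing values could not be imputed, or that the protocol should say how.** Baseline EQ-5D and serial acuity, contrast sensitivity and CAT scores are usable predictors, and the method belongs to an analysis plan that is not shown.

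All of this stands, and so does a limit on the remedy: a patient who withdraws fully is not reached by a remote link. What remains is that the trial's only follow-up utility is a single reading, with no stated recovery route, in a model that accrues QALYs partly by adherence status.

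**Conclusion.** The concern holds as a limited weakness in data collection. No stated figure is wrong and no two sections conflict. Up to 40 of 200 patients could have no post-baseline EQ-5D at the planned maximum dropout. Under assumed mixes from 30% to 100% non-adherent among dropouts, that is 20% to 67% of the expected non-adherent patients. Under the assumed deficits, a completers-only comparison could overstate the month-18 utility difference by 0.0025 to 0.005, leave it unchanged, or understate it by 0.005 to 0.02, against an expected difference of 0.01 to 0.02. The sign cannot be determined from the documents. The consequence is confined to the month-18 weights and the trial-period QALYs. It is worth correcting because it is cheap now and cannot be repaired after follow-up has passed.

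**What to change.** In Section 5, add EQ-5D to the CAT link already sent at months 6, 12 and 18, keep the baseline assessment, and name EQ-5D in the remote invitation and in the next-visit contact for patients who miss the window, recording the date of completion. In Section 8.2 (Specific aim 4), state that the trial-period QALYs use all available EQ-5D readings rather than month 18 alone. Treatment of values still missing can be left to the statistical analysis plan.

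The cost is one short questionnaire at two more time points and for non-attenders, on a link that already exists: slightly more burden for patients, no extra visit or staff, and no change to the sample size. Patients who withdraw fully would still lack a month-18 value, although many would then have a reading from month 6 or 12.
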